## 1. Background

### 1.1 Introduction

This is a single center study to ascertain dosing and tolerability of add-on (i.e., in addition to their standard anti-epileptic therapy) Cannabidiol in children between 12 months and 18 years with treatment-resistant epilepsy due to Dravet syndrome. Dravet syndrome is a devastating syndrome which causes medication resistant epilepsy associated with significant cognitive morbidity and frequent seizures [1-7]. In addition to the significant morbidity, children with refractory epilepsy are at risk of seizure-related mortality and Sudden Unexpected Death in an Epilepsy Patient (SUDEP) [8]. The risk of SUDEP in treatment resistant epilepsy is 1 in 150 [9]. The current armory of anti-epileptic drugs, dietary therapy and the Vagal Nerve Stimulator (VNS) device are not always successful in achieving seizure control. The healthcare costs of childhood-onset treatment resistant epilepsy are well established [10, 11]. In Dravet syndrome the severity of the epilepsy often requires frequent emergency department attendances, and hospital admissions.

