were observed to have significant reduction in seizures after 3 months. The range of seizure reduction was found to be 55% to 100% with a mean of 90%. 10 of 11 patients experienced 80% or more seizure reduction, and 3 of 11 patients were seizure free after 3 months of therapy. The average dose giving maximal improvement at 3 months was 5 mg CBD/lb/day (range: 2-8 mg CBD/lb/day or 1-3.6 mg/kg/day). Families reported no adverse effects attributed to the high CBD, low THC extract therapy. Several families reported an increase in adverse events from concurrent AEDs, including irritability and increased seizure activity, when therapy was added. Families reported that titrating down doses of concurrent AEDs while continuing therapy resolved adverse events and improved seizure control.

The CBD/epilepsy landscape was further changed dramatically in December 2015 with the publication by Devinsky and colleagues [32] of an open-label trial of CBD, in over 200 patients (aged 1–30 years) with severe, intractable, childhood-onset, treatment resistant epilepsy, in 11 epilepsy centers across the United States. Open label add-on study, 11 centers across US between 2014-2015. The CBD used in this study was a 99% pure oil-based cannabidiol extract of constant composition (Epidiolex, GW Pharmaceuticals, London, UK), in a 100 mg per mL preparation, so 100:1 ratio of CBD:THC. Their results showed an average reduction from 30 seizures a month to 16 seizures a month. There were 5 participants who were free from motor sz at the end of the 12 weeks. They titrated doses up to 25mg/kg/day without patients withdrawing due to side effects. They noted that side effects of GI disturbance (diarrhea) were more likely at higher doses, and they titrated up to 25mg/kg/day.

Health Canada has approved a cannabis extract oil of 18:1 ratio CBD:THC and 20:1 CBD:THC for sale to patients of all ages (Cannimed licensed producers). Given the recent data on CBD:THC at a 100:1 ratio from Devinsky et al (Epidiolex)[32], we feel dosing and safety for a 50:1 CBD:THC cannabis extract product in our study product is the appropriate next step. This ratio allows us to maximize the CBD dosing, while ensuring exposure to lower THC dosing than products currently licensed for sale to patients in Canada.

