#### **4. Selection and Withdrawal of Participants**

##### **4.1 Inclusion Criteria**

Participants selected for the study must meet the following criteria:

1. Age between 12 months and 18 years
2. Parent/ legal guardian informed consent obtained
3. Clinical and EEG (sleep recording within 12 months of study enrollment) characteristics of Dravet Syndrome and confirmatory genetic mutation result
4. Medication-resistant epilepsy – with failure to achieve seizure control with at least 2 appropriate AEDs at therapeutic doses
5. Clinically apparent seizures (excluding myoclonic and absence) occurring at least twice per week
6. Agreed diary compliance and clinical compliance with current prescribed therapy
7. Concomitant AED medication dosing stable during 4 week pre-intervention period. Ketogenic diet regime and VNS device settings must be stable for 3 months prior to pre-intervention period.
8. Ability to tolerate administration of medication orally or via percutaneous feeding tube (PEG).
9. Negative urinary pregnancy test for all female participants of child bearing age

10. Was never on Cannabinoid therapy or have not been treated with Cannabinoid products for at least last 60 days (confirmed by negative urine test for Tetrahydrocannabinol (THC), only for those who had been treated with CBD).

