## **7. Assessment of Safety and Adverse Events**

### 7.1 Specification of Safety Parameters

Each participant will be carefully screened for suitability prior to commencement of the intervention. If the study team feels that any pre-existing conditions place the participant at risk they will be excluded from participation. Once enrolled in the study each participant and parent/legal guardian will receive education regarding the administration, dosing and schedule of the study treatment from the study investigator physician, study nurse and the study pharmacist. This information will be reviewed and dosing schedule re-evaluated at every clinic visit and phone call / email follow up. During each clinic visit there will be an evaluation of tolerability of the study treatment and of possible adverse events.

If at any stage during the study any adverse events are suspected they will immediately be evaluated by study team. The adverse event reporting period is from the initiation of the study treatment until the end of study treatment follow-up.

An *adverse event* is any symptom, sign, illness or experience that develops or worsens in severity during the course of the study. Intercurrent illness or injuries should be regarded as adverse events. Abnormal results of diagnostic procedures are considered

adverse events, if the abnormality leads to study withdrawal, is associated with clinical signs or symptoms, leads to additional treatment or diagnostic tests, is considered by the study team to be of clinical significance or is considered a serious adverse event.

*A serious adverse event* is one which is:

- fatal
- life-threatening
- requires hospitalization or prolongs hospital stay
- results in persistent or significant disability or incapacity
- a congenital anomaly or birth defect
- an important medical event (not immediately life-threatening but of significant clinical importance)

All adverse events that do not meet the criteria for seriousness should be considered *non-serious adverse events*.

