## **8. Statistics**

### **8.1 Statistical Method**

This is an observational study. The primary aims of this study are to determine the tolerability of the study treatment in a cohort of children with medication resistant epilepsy due to Dravet syndrome. As such, there are no formal statistical methods required, rather descriptive statistics will be presented to quantify dosing tolerability and frequency of adverse events. All participants will be analyzed regardless of dose achieved or duration of study completed, according to intention to treat analysis. The study data will be entered into the REDCap database for analysis.

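### The adverse-event definition in section 7.1 leaves out frequency, so an existing episodic symptom that only becomes more frequent is not counted in the adverse-event summary

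*Combined protocol and SAP*

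**What the plan says.** Section 7.1 defines an adverse event as "any symptom, sign, illness or experience that develops or worsens in severity during the course of the study". It adds that "Intercurrent illness or injuries should be regarded as adverse events" and gives separate criteria for abnormal test results. On timing it says: "The adverse event reporting period is from the initiation of the study treatment until the end of study treatment follow-up". One criterion for a serious event is that it "requires hospitalization or prolongs hospital stay". Section 7 has no rule for seizures, for a rise in seizure frequency or for seizure admissions.

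The children enter with frequent events. Inclusion criterion 5 (section 4.1) requires "Clinically apparent seizures (excluding myoclonic and absence) occurring at least twice per week", and section 1.1 says: "In Dravet syndrome the severity of the epilepsy often requires frequent emergency department attendances, and hospital admissions".

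Adverse events feed the main analysis. Section 8.1 says that no formal methods are needed, "rather descriptive statistics will be presented to quantify dosing tolerability and frequency of adverse events". The Study Summary plans the frequency and severity of adverse events for the dosages used.

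**The concern.** The definition has two ways in: something new, or something existing that becomes more severe. A symptom that was present before treatment and then occurs more often, with each episode no worse, fits neither.

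This matters because many of the harms the plan expects are episodic. Sections 1.2 and 1.7.1 name vomiting or gastrointestinal disturbance, falls and nose bleeds. Section 1.2 also presents several of its listed effects as common with anti-epileptic drugs, and these children take one to four such drugs. Some may therefore have these symptoms before the first dose.

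The primary endpoint is the maximal safely tolerated dose (section 3.4). If an existing symptom starts to occur more often at a higher dose, the adverse-event table shows nothing against that dose. The product would then look cleaner in the children with the most background symptoms.

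**Working it through.** The plan gives no expected adverse-event count and no sample-size calculation (section 8.2), so there is no figure to reproduce. The check is to compare the passages.

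**1. Does severity include frequency in this plan?** Section 6.2 measures seizure frequency by diary counts. It measures seizure severity by rescue medication use, status epilepticus, and emergency attendance or hospitalisation. A plain rise in seizure count belongs to the first measure, not the second. Section 7.1 names only severity.

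**2. What happens to one child?** As an illustration, take a child at the entry minimum of 2 seizures a week who rises to 4 a week at unchanged severity for 20 weeks. The extra seizures number (4 − 2) × 20 = 40. The diary shows all 40. Under section 7.1 as worded, none is an adverse event.

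**3. Is that consistent with the rest of the plan?** Section 4.4.1 lists unexplained seizure exacerbation as a possible reason for discontinuation. A child could be withdrawn for more frequent seizures without clearly meeting the adverse-event definition.

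**4. Do other records fill the gap?**
- *Seizures:* largely yes. The 4-week baseline diary (section 5.5) and the continuing diary hold the counts, status epilepticus, rescue use and admissions. Section 7.2 has the team review the diary but does not link it to adverse-event recording.
- *Injuries:* yes. They count under section 7.1 whatever the earlier pattern, so a fall that causes injury is recorded.
- *Other episodic symptoms:* no. The diary does not cover them. The Pediatric Epilepsy Side Effects Questionnaire (PESQ) first appears at Week 2 in sections 5.6 and 5.8. Section 7.2 asks for it at every clinic visit, which could be read to include Week 0, but neither the Week 0 text nor the schedule lists it. The history in section 5.5 covers seizures, medications, birth and development. The adverse-event window opens only at the first dose.

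**5. Can the loss be sized?** Among children in whom the product makes a symptom more frequent, let *b* be the share who already had it and *s* the share of those whose severity is unchanged. Under the definition as worded, the share missed is *b* × *s*. The documents give neither value, so the result can lie anywhere from 0 to 1.

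**The case against.** The strongest reply is that little is hidden. The primary objective (section 2) also rests on bloodwork, drug levels, caregiver report, physician assessment and the PESQ. Relevant symptoms go into source documents (section 7.3). One team at one centre collects the data, the investigators review safety after every third patient (section 1.5), and the principal investigator reviews the documentation (section 10). A sensible recorder might also treat a new run of frequent vomiting as an experience that has developed. In section 1.4, on a cited retrospective review, the authors write: "Several families reported an increase in adverse events from concurrent AEDs, including irritability and increased seizure activity". That suggests they would regard more seizures as adverse.

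Much of this stands: an increase would probably be seen. It does not settle whether the increase is counted. Section 1.4 reports another study and sets no rule here. Section 6.2 does use frequencies to measure seizure severity, which softens the distinction. But that measure is not carried into section 7, leaves out a plain rise in seizure count, and does not apply to non-seizure symptoms.

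A reader might infer the opposite fault: that each seizure develops during the study, so every usual seizure is an adverse event and every usual seizure admission a serious one. Multiplying the entry rate by weeks and children would then give a very large count. The documents do not support this. The seizure pattern is an entry requirement, seizures are assigned to the diary and reported as secondary outcomes, and nothing says each is logged as an adverse event.

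**Conclusion.** The definition should be corrected. As worded, it leaves out an existing problem that becomes more frequent at unchanged severity, while the frequency of adverse events is a primary descriptive output. The effect is confined to the adverse-event tabulation and falls mainly on non-seizure episodic symptoms.

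The conclusion assumes that recorders apply section 7.1 literally and that some children have such symptoms before treatment. The first is a reading of the text; the second is plausible but not quantified in the plan.

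A reader might want a percentage undercount. Any such figure would only restate the assumed baseline prevalence and assumed effect. Nor do the documents support the view that seizure worsening would be lost, since the diary retains it.

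**What to change.** Reword section 7.1 so that an adverse event is one that *develops, or worsens in severity or frequency compared with the child's pre-treatment pattern*. For seizures, take that pattern from the 4-week baseline diary. For other symptoms, take it from a caregiver history recorded before the first dose. How large a rise counts is for the investigators to set.

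State that seizures within the baseline pattern are recorded in the diary only. Tabulate status epilepticus and seizure hospitalisations separately from other serious events, because admissions are common in this disease and the hospitalisation criterion has no rule for them. These counts are already collected as secondary measures, so this changes only the presentation.

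The cost is a few sentences in section 7.1, a short history before the first dose and an extra table row. The downside is that some additional non-serious events will be recorded.

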## 7.2 Methods of assessing

During the intervention period and follow-up there will be regular clinic review and telephone/email evaluation of the participant to assess tolerability of the study treatment and screen for any adverse events. This will be done by direct questioning of participant, parent/caregiver at each review. In addition the study team will perform a physical and neurological examination of participant at each clinic review. Every clinic visit we will ask parent/ caregiver to complete a side effect questionnaire (PESQ questionnaire) and study team will review the daily seizure diary. In addition at regular

intervals during the study the participant will have bloodwork to evaluate hematopoiesis, liver and renal function and trough AED levels.

### 7.3 Recording Procedures

At each contact with study participant the study team will evaluate for potential adverse events as specified above. Information on all adverse events will be recorded immediately in source document (medical chart) and in the specific adverse event case report form (CRF). All relevant symptoms, signs, and abnormal diagnostic tests will be recorded in the source documents also.

### 7.4 Reporting Procedures

#### Adverse Event Reporting to the SickKids REB and to Health Canada

All adverse events will be reported to The Hospital for Sick Children Research Ethics Board according to The Hospital for Sick Children's Adverse Event Reporting Requirements. All serious, unexpected adverse drug reactions (S-UADR) will be reported to Health Canada within 15 calendar days or for death or life-threatening events, within 7 calendar days. In the latter case, a follow-up report must be filed within 8 calendar days. Adverse reactions will be managed according to The Hospital for Sick Children's standard clinical management practices. Each ADR which is subject to expedited reporting should be reported individually in accordance with the data element(s) specified in the Health Canada/ICH Guidance Document E2A: Clinical Safety Data Management Definitions and Standards for Expedited Reporting.

### 7.5 Adverse Event Follow-up

The clinical course of each adverse event encountered will be followed by the study team until resolution, stabilization, or until determined that study participation is not

causative. Serious adverse events that are ongoing at the end of the study period will continue to be followed until they are either resolved, or in the opinion of the Principal Investigator, the participant is medically stable and does not require further follow-up or the participant is deemed lost to follow-up. Any serious adverse event that occurs after the intervention period, but is deemed by the study team as possibly related to participation will be recorded and reported also.

## **8. Statistics**

### **8.1 Statistical Method**

This is an observational study. The primary aims of this study are to determine the tolerability of the study treatment in a cohort of children with medication resistant epilepsy due to Dravet syndrome. As such, there are no formal statistical methods required, rather descriptive statistics will be presented to quantify dosing tolerability and frequency of adverse events. All participants will be analyzed regardless of dose achieved or duration of study completed, according to intention to treat analysis. The study data will be entered into the REDCap database for analysis.

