## Study Summary

|                                       |  |
|---------------------------------------|--|
| Title                                 | Cannabinoid Therapy in Medically Refractory Pediatric Epilepsy – Phase 1: Dosing and Tolerability Study of a Cannabidiol-Rich Whole Plant Extract of Cannabis.   |
| Short Title                           | Cannabinoid Therapy for Pediatric Epilepsy   |
| Phase                                 | 1  |
| Methodology                           | Open-label Intervention  |
| Study Duration                        | 20 weeks to primary analysis with continued follow-up until 64 weeks completed   |
| Study Center                          | The Hospital for Sick Children, Toronto Ontario  |
| Objectives                            | To determine the tolerability and optimal dose of 50:1 ratio CBD:THC Cannabis extract as an adjunct treatment in children with severe drug resistant epilepsy  |
| Number of Subjects                    | 20   |
| Diagnosis and Main Inclusion Criteria | Patients with Dravet Syndrome

Between ages of 1 and 18 years old male or female

Must have failed 2 AEDs at therapeutic doses and be on current regimen of 1-4 AEDs which have been stable doses for 4 weeks  |
| Study Product, Dose, Route, Regimen   | TIL-TC150 Oil is the study product
The active ingredients in TIL-TC150 Oil are THC and CBD, present in a 1:50 ratio. These active ingredients are derived from Cannabis sativa L. strains produced by Tilray and suspended in a grape seed oil. This suspension is administered at a dose of 2mg/kg/day CBD divided BID and titrated up to a maximal dose of 16mg/kg/day CBD (or maximal tolerated). |
| Duration of Administration            | Study period: primary safety and outcome data at 20 weeks with longer follow-up of safety and tolerability in those who chose to continue after the 20-week period and will be followed up to 64 weeks.  |
| Reference Therapy                     | None   |
| Statistical methodology               | The primary aims of this study are to determine the maximal tolerated dose of TIL-TC150 Oil Cannabis Extract in children with drug resistant epilepsies. Descriptive statistics will be used to quantify the frequency and severity of adverse events that are   |

|  |  |
|--|--|
|  | reported for the various dosages that are employed |
|--|--|

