### **3. Study Design**

The study is a Phase 1 dosing and tolerability study of TIL-TC150. TIL-TC150 will be administered to 20 children with Dravet syndrome by the investigator team who will closely follow them for the duration of the study.

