### 3.2 Intervention period (20 weeks)

Following the pre-intervention assessment of baseline seizure frequency, the participant will commence TIL-TC150 product. The initial dose is 2mg/kg/day CBD divided twice daily with weekly titration as described below in section 5. Study treatment will be increased each week as tolerated by 2mg/kg/day CBD. Week 8 should be the last increase if the participant increases by this schedule. The maximal dose is 16/mg/kg/day CBD.

During this time there will be regular communication and clinic visits with the investigator team, as detailed in section 5. Once 16 weeks of therapy have been completed, participants will enter a 4 week interim analysis period, during which time they continue the TIL-TC150 at an unchanged dose and a 4 week seizure diary and a 24 hour ambulatory EEG recording will be performed and compared with the pre-intervention seizure frequency.

This primary outcome data regarding safety, tolerability, dosing and secondary seizure outcomes will be reported at this time point.

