### 3.4 Primary Study Endpoint

The primary endpoint is establishing the maximal safely tolerated dose of TIL-TC150 in our study population.

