### 5.2 Treatment Regimen

Each participant will start the treatment with a dose of 2mg/kg/day CBD given in two equal doses each day. The first dose will be given during the Baseline (Week 0) visit. Following this dose the participant will be observed by study personnel for a period of 2 hours. The participant's parent/legal guardian will increase the participant's dose by 2mg/kg/day CBD every 7 days as tolerated, to a maximal dose of 16mg/kg/day CBD. Once optimal dose is determined for each participant they may continue the treatment for the duration of study follow-up and thereafter it will be continued if wished by participants.

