### **8.2 Sample Size**

No sample size calculation was employed. An intermediate sample size of convenience is selected, with 20 participants expected to be recruited from a single site.

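### Section 8.1 mislabels an interventional Phase 1 titration trial as observational, plans no measure of precision for tolerability and adverse events in 20 children, and gives no analysis for the before/after outcomes

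*Combined protocol and SAP*

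**What the plan says.** Section 8.1 opens "This is an observational study", gives tolerability in Dravet syndrome as the primary aim, and then concludes that "there are no formal statistical methods required, rather descriptive statistics will be presented to quantify dosing tolerability and frequency of adverse events". It adds that every participant is analysed whatever dose or duration was reached.

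Other sections describe a different kind of study. The Study Summary gives the methodology as "Open-label Intervention" with no reference therapy. Section 3 states "The study is a Phase 1 dosing and tolerability study of TIL-TC150". Section 5.2 has the protocol set the starting dose, the weekly steps and the ceiling: "Each participant will start the treatment with a dose of 2mg/kg/day CBD given in two equal doses each day".

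Section 3.4 sets the goal: "The primary endpoint is establishing the maximal safely tolerated dose of TIL-TC150 in our study population". Section 8.2 reports that no sample size calculation was made: "An intermediate sample size of convenience is selected, with 20 participants expected to be recruited from a single site".

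Section 2 lists quality of life (QOLCE), adaptive behaviour (Vineland), diary seizures and EEG activity as secondary measures. Section 3.2 says that the diary and EEG from weeks 16 to 20 will be "compared with the pre-intervention seizure frequency", and Section 6.1 commits to reporting the change. Section 8 does not mention any of these outcomes.

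**The concern.** There are three related faults.

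- **The label is wrong.** A study that assigns a product and titrates it by protocol is not observational.
- **The primary results have no planned precision.** Section 3.4 asks for a conclusion about a safely tolerated dose. Counts and percentages from about 20 children cannot carry that conclusion unless the reader is told which true rates remain compatible with them.
- **The before/after outcomes have no analysis.** The plan does not say which summary of change will be used, over which children, or with what interval.

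At stake is how firmly words such as safe and tolerated can be used in the report. A zero count could be taken as showing that an event does not occur. A fall in seizures could be given as one number with nothing to show its uncertainty.

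**Working it through.** **What can be reproduced.** Section 8.2 gives N = 20 by convenience. The documents state no alpha, power, effect size, SD, target rate or margin, so 20 cannot be re-derived. The check is therefore what 20 children can show.

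**Inputs.** N = 20 (Section 8.2). Reference rates from the open-label study cited in Section 1.7.1: somnolence 25%, status epilepticus 6%, diarrhea as a serious adverse event 2%. The 95% level is an assumption, because the plan states none.

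**Step 1: exact (Clopper-Pearson) limits for x/20.** The lower limit is the 0.025 quantile of Beta(x, 21 − x). The upper limit is the 0.975 quantile of Beta(x + 1, 20 − x). For x = 0 the upper limit reduces to 1 − 0.025^(1/20) = 0.168. The one-sided 95% bound is 1 − 0.05^(1/20) = 0.139.

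| Observed | Exact 95% limits |
|---|---|
| 0/20 | 0 to 16.8% |
| 1/20 | 0.1% to 24.9% |
| 2/20 | 1.2% to 31.7% |
| 5/20 (25%, the cited somnolence rate) | 8.7% to 49.1% |
| 10/20 | 27.2% to 72.8% |
| 20/20 | 83.2% to 100% |

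**Step 2: chance of seeing no case among 20, (1 − p)^20.**

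- p = 6%: 0.94^20 = 0.29.
- p = 2%: 0.98^20 = 0.67.

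A zero count is therefore quite possible for events that the protocol itself lists as risks.

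**Step 3: results by dose.** The Study Summary plans adverse events by dosage. Titration is within child and as tolerated (Section 5.2), and withdrawals are not replaced (Section 4.4.3), so fewer than 20 children may reach the higher steps. If 16 reach a step (an assumption), 0/16 gives an upper limit of 20.6%. If 15 do, it is 21.8%. These children are also selected, because they tolerated the lower steps.

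**Step 4: before/after change.** For a mean paired change the 95% half-width is t(0.975, n − 1)/√n in units of the SD of the change. That is 0.47 SD with 20 pairs, and 0.53 SD if 16 children have both diaries (an assumption). For a median change with n = 20, the 6th and 15th ordered values form an interval with coverage 1 − 2·P(Bin(20, 0.5) ≤ 5) = 95.9%.

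**Step 5: choice of scale.** A log ratio of seizure rates is undefined for a child with no seizures in weeks 16 to 20, and Section 1.4 describes seizure-free children in earlier reports. Percentage change is then simply −100%. The diary baseline should not be zero, since Section 4.1 requires at least two seizures per week, or about 2 × 4 = 8 in four weeks. A 24-hour EEG is different: two per week is 2/7 = 0.29 per day, so a baseline recording may contain no seizure. The percentage change in electrographic seizures named in Section 2 would then be undefined.

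**The case against.** The strongest reply is that this is a small Phase 1 study without a comparator, for which descriptive reporting is normal. That stands: no hypothesis test is needed, and the lack of one is not the fault.

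A reader might infer that formal methods were dropped because the study was called observational. The text does not establish this. The conclusion in Section 8.1 follows directly on the tolerability aim as well as the label, and that aim is an ordinary ground for a descriptive plan. Removing the label would leave the plan as it is. Other sections leave the design in no doubt, so the label is an error to correct and not a proven cause.

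A reader might also infer that the plan decides to report everything without uncertainty. It does not say so. Descriptive statistics do not rule out intervals, and for seizures, EEG, QOLCE and Vineland Section 8.1 is silent. The fault there is a missing analysis and not a declared choice.

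No dose decision or success criterion in the documents depends on an interval, Section 6.1 says efficacy is not primary, and anyone given n/N can compute the limits. These points lower the stakes for conduct. They do not excuse leaving precision unplanned when the stated goal is a conclusion about safety.

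Two limits of the remedy also stand. Neither Section 3.4 nor Section 8.1 gives a countable definition of tolerated, and an interval does not supply one. Intervals also cover sampling error only. They do not address regression to the mean or open-label parental reporting.

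**Conclusion.** The point holds in this form: the study type is mislabelled, no precision measure is planned for tolerability and adverse events, and the committed before/after outcomes have no specified analysis. The documents do not support the stronger claims that the label caused the descriptive plan or that intervals were ruled out.

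The size is material for a trial meant to establish a safely tolerated dose. An event seen in none of 20 children may still occur in up to 16.8% (13.9% one-sided). A 25% observed rate spans 8.7% to 49.1%. Even if all 20 tolerate treatment, a true proportion of 83.2% remains compatible.

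These figures assume 95% confidence, independent children, and all 20 in the denominator. Smaller denominators widen them. The 29% and 67% chances of seeing no case further assume that the cited study's rates apply to this population. Trial conduct and data collection are unaffected. What changes is how firmly the conclusions can be worded.

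**What to change.** 1. In Section 8.1, describe the study as a single-arm, open-label interventional trial and keep the analysis descriptive, without hypothesis tests.
2. Report each adverse event and tolerability proportion as n/N with an exact (Clopper-Pearson) 95% interval, giving the upper limit when the count is zero. State how tolerated is counted, as the sponsor defines it. For dose-level results, use the number of children who reached that level as the denominator and note that they had tolerated the lower levels.
3. Summarise within-child change from the 4-week baseline to weeks 16 to 20 as the median percentage change in 28-day seizure rate, and as the median change for EEG, QOLCE and Vineland. Give each a 95% interval. The order-statistic interval matches the median directly; Hodges-Lehmann is an alternative where changes are roughly symmetric. Report how many children have both measurements and how missing diaries are handled. Label these results exploratory and uncontrolled.
4. In Section 8.2, state what 20 children can exclude (0/20 excludes only rates above 16.8% at two-sided 95%), and keep safety conclusions within that limit.

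The cost is a few sentences in Sections 8.1 and 8.2 and minor programming, with no new patients, visits or data. The results will look less definite.
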